5.0 Procedures Involved

5.1 Study Design:

This is a triple-blind, randomized placebo-controlled clinical trial (with blinded subjects, experimenters and statisticians) with healthy controls (cohort 1) and schizophrenia patients (cohort 2). 90 HCs, after signing consent and determining eligibility will be enrolled and randomized to receive either (i) Active 2mA right (AF4

PROTOCOL TITLE: Increased thalamocortical connectivity in tDCS-potentiated generalization of cognitive training

VERSION DATE: January 26, 2023

anode-AF3 cathode) or (ii) Active 2 mA left (AF3 anode-AF4 cathode), or (iii) Sham 0 mA tDCS during concurrent WM focused training for a total of 12 weeks. 90 SZ patients, after signing consent and determining eligibility will be enrolled and randomized to receive either (i) Active 2 mA left (AF3 anode-AF4 cathode), or (ii) Sham 0 mA tDCS during concurrent WM focused training for a total of 12 weeks. For the active stimulation, current will ramp-up for 30 seconds, remain at 2mA for 20 min and then ramp-down for 30 seconds at the end of the stimulation session. For sham stimulation, the electrodes will be placed at the same positions as for active stimulation (AF3 and AF4), but current will be turned off immediately after the initial 30 second ramp-up period. Thus, participants will feel the initial itching sensation associated with tDCS but will receive no active current for the rest of the stimulation period. This method of sham stimulation has been shown to be reliable(Gandiga, Hummel, & Cohen, 2006). To test the effects of dosage, we have scheduled a midtest and MRI scan after 6 weeks of training (approximately 15 sessions), and a posttest and scan at the completion of the protocol after 12 weeks (approximately 30 sessions). The assessment battery will be completed again at follow-up 12 weeks after the final training session.

5.2 Study Procedures:

Pre-Screening for Cohort 1 (healthy controls): Study staff or weblinks will direct interested individuals to a HIPAA compliant online portal with a thorough description of the requirements of the study. At this time, interested individuals will answer relevant screening questions, including tDCS or MRI contraindications. Volunteers will also complete items from a neuropsychological vocabulary test to estimate crystalized IQ. If the HC volunteer fulfills inclusion and exclusion criteria, they will be invited to participate and scheduled for the pretest assessment.

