Assessment activities may be audio/video-recorded. These data will be reviewed by the study team in order to achieve reliability and consistency between different interviewers and to arrive at consensus ratings for assessment scores. Assessment audio/video data will be stored on a secured UMN Box server and will only be accessible by the study team. Participants will have the choice to opt out of assessment audio/video recording in the consent form.

In addition, all participants will provide a urine or saliva sample in order to complete a drug screen. Results will be recorded.

HC participants will be randomly assigned to one of the 3 groups: (i) Active 2mA right (AF4 anode-AFP3 cathode) or (ii) Active 2 mA left (AF3 anode-AFP4 cathode), or (iii) Sham 0 mA tDCS during concurrent WM focused training for a total of 12 weeks. SZ participants will be randomly assigned to one of the 2 groups: (i) Active 2 mA left (AF3 anode-AFP4 cathode), or (ii) Sham 0 mA tDCS during concurrent WM focused training for a total of 12 weeks. Neither participants nor experimenters will know group assignment. TDCS software programming will allow staff selection of the three hemisphere conditions (right, left, sham) corresponding to eight random letters (six to be distributed evenly among three conditions for HCs, two to be distributed evenly among two conditions for SZs) encoded to preserve the blind. Randomization will be facilitated and the blinding code will be maintained by the study statistician.

Neuroimaging Assessments/MRI (Baseline, Week 6, Week 12):

Participants who are able to do in-person study visits will complete MRI sessions using the 32 channel head coil on a 3T Siemens Prisma scanner (Siemens Erlangen, Germany) located in the Center for Magnetic Resonance Research (CMRR) at the University of Minnesota at baseline, midway through the intervention and post-intervention, at 12 weeks. MRIs will not be completed if there is any concern for participant safety. This includes safety concerns during the COVID-19 pandemic.

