
Analyses to test SA2, that generalization and durability are driven by right tDCS more than left tDCS or sham (H2.1), longer treatment length (H2.2) and higher modeled dosage (H2.3) will be conducted both between and within groups (for both Studies 1 and 2). The first step will establish the existence of between-group training effects using repeated-measures ANOVA’s on the key performance outcome variables (d' scores for the word and picture N-backs, d'-context for the DPX, and the composite score for MCCB). We will also evaluate differences in self-rated engagement and experimenter-rated Work Behavior Inventory (Bryson et al., 1997), sleep patterns, age, baseline IQ, and these will be used as covariates of non-interest as appropriate.

PROTOCOL TITLE: Increased thalamocortical connectivity in tDCS-potentiated generalization of cognitive

training

VERSION DATE: January 26, 2023

To examine SA3, the relationship between thalamocortical FC change and generalization and durability, we will examine the nonparametric relationships between changes in thalamocortical connectivity and improvements on the trained task (word N-back d'), proximal transfer (picture N-back d'), and more distal generalization (DPX d', MCCB composite score) and durability (H3.1 and H3.2 respectively). If analysis of covariates suggest that there are important sources of within-group variance in learning (e.g. age, baseline IQ, etc.), then hierarchical regressions will be used on Fisher's transformed z-scores of thalamocortical connectivity. In addition, to determine whether thalamocortical FC changes predict stability in learning and generalization, task performance at 24 weeks will also be subjected to hierarchical regressions. The regression model will enter covariates on step 1, and thalamocortical connectivity on step 2. The statistician will be blind to condition until analyses are completed.

In all cases, these relationships will be tested separately for Cohort 1 and Cohort 2, as changes associated with improvement are likely to be different for groups with different mean levels of ability. Follow-up analyses will determine the extent to which these observed differences suggest actual differences between these populations. However, the current study is not designed to directly compare the populations.

15.2 Power Analysis:

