75 completers in cohort 1 and cohort 2 will provide power of .80 to detect effects as small as $\eta^2=.03$ for key confirmatory analyses (tested at $\alpha = .05$) and $\eta^2=.05$ for other analyses (tested at $\alpha=.005$), with nearly as strong power for the analysis of the 24 week follow-up. The more conservative approach of intent-to-treat analysis ($n=90$) will also be conducted for Cohort 2, for which the study will be sensitive to $\eta^2=.027$ (tested at $\alpha = .05$) and $\eta^2=.042$ (tested at $\alpha = .005$). These effect sizes are much smaller than the group x time effect for generalization as measured by the MCCB in our pilot tDCS data ($\eta^2=.08$), suggesting the proposed study is well-powered. While power analyses for neuroimaging studies are challenging due to the interactions of voxelwise-thresholds, brain-wise error correction and spatial smoothness, the proposed studies will be well-powered to detect group x time voxel differences as small as $\eta^2=0.07$ (tested at $\alpha = .001$), and in any case the samples are twice the size of our previous, successfully replicated, neuroimaging studies of brain change following cognitive remediation. Within-group responder analyses conducted for completers ($n=25$ per cell) will have power of .80 to detect correlations $r \geq .34$, a lower magnitude than we already observed ($r=.55$).

15.3 Statistical Analysis:

See section 16.1

15.4 Data Integrity:

The investigator is responsible for ensuring the accuracy, completeness, legibility, and timeliness of the data reported. To enhance scientific rigor, avoid bias and enhance reproducibility, our triple-blind randomized design will use a stratified permuted block randomization procedure (Matts & Lachin, 1988) to roughly equate age and baseline WM performance across groups with a block size of 6. Neither participants nor experimenters will know group assignment. TDCS software programming will allow staff to randomly select one of the three hemisphere conditions (right, left, sham) corresponding to eight letters (six to be distributed evenly among three conditions for HCs, two to be distributed evenly among two conditions for SZs) encoded to preserve the blind. Randomization will be facilitated and the blinding code will be maintained by the study statistician.

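### Section 15.2: with 25 per cell, power .80 is reached at a correlation of about .53 (two-sided .05 assumed), not .34, and 25 per cell does not fit the two-arm Cohort 2

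*Combined protocol and SAP*

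**What the plan says.** Section 15.2 (Power Analysis) says: "Within-group responder analyses conducted for completers ($n=25$ per cell) will have power of .80 to detect correlations" of .34 or larger. It adds that this is "a lower magnitude than we already observed ($r=.55"), the pilot value reported in section 2.2. The sentence states neither alpha nor sidedness. Earlier in the same paragraph, key confirmatory analyses are given alpha .05, and a second level is set "for other analyses (tested at $\alpha=.005").

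The cell size appears to come from the opening of 15.2: "75 completers in cohort 1 and cohort 2 will provide power of .80 to detect effects as small as" the stated eta-squared values. I read 75 as the number per cohort, because each cohort enrols 90 and 15.2 gives an intent-to-treat n of 90 for Cohort 2 alone.

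On the analysis itself, section 15.1 says for SA3 that "we will examine the nonparametric relationships between changes in thalamocortical connectivity and improvements on the trained task" and on transfer measures, and that "these relationships will be tested separately for Cohort 1 and Cohort 2". On the design, section 5.1 has "90 SZ patients, after signing consent and determining eligibility will be enrolled and randomized to receive either (i) Active 2 mA left" or sham, and section 5.2 repeats that "SZ participants will be randomly assigned to one of the 2 groups". Cohort 1 has three arms. Section 4.1 expects Cohort 2 to end up smaller than planned, without giving a number.

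**The concern.** A correlation of .34 is small for 25 observations. At n = 25 a sample correlation has to reach .396 to be significant at two-sided .05, or .337 at one-sided .05. A true value of .34 therefore has at best about an even chance of significance, which cannot be reconciled with power of .80.

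A reader who trusts the sentence would take a non-significant per-arm result as fair evidence that connectivity change and cognitive gain are unrelated in that arm. SA3 is listed under the primary endpoints in section 3.1, and variability of response within both groups is part of the stated purpose, so such a reading is likely. The comparison with .55 also suggests a comfortable margin over the pilot, which the design does not have.

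Two further points bear on the n. The cell size assumes three arms, and Cohort 2 has two. In addition, section 5.2 defines completion by number of sessions, while section 5.7 lets remote participants go without MRI, so a completer may have no connectivity change to correlate.

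**Working it through.** **Inputs.** n = 25 per cell, power .80, stated limit r = .34, pilot r = .55, alpha .05 and .005, 75 completers (all in 15.2). Arms: three in Cohort 1, two in Cohort 2 (5.1, 5.2). Assumed, because not stated: alpha .05 for this analysis. Both one- and two-sided tests were tried.

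**Step 1: try to reproduce .34.** With Fisher's z, the smallest detectable correlation is r = tanh[(z_alpha + z_power)/√(n − 3)].

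- Two-sided .05: (1.960 + 0.842)/√22 = 0.597, so r = .535.
- One-sided .05: (1.645 + 0.842)/√22 = 0.530, so r = .486.
- Two-sided .005: (2.807 + 0.842)/√22 = 0.778, so r = .65.

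An exact bivariate-normal calculation (noncentral t averaged over the distribution of the predictor) gives slightly lower limits:

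| n = 25, Pearson | limit for power .80 (exact) | power at r = .34 |
|---|---|---|
| two-sided .05 | .53 | .39 |
| one-sided .05 | .48 | .52 |
| two-sided .005 | .65 | .12 |

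No row gives .34. For .34 to have power .80 at n = 25, alpha would have to be about .37 two-sided or .19 one-sided.

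**Step 2: n needed for r = .34.** n = [(z_alpha + z_power)/atanh(.34)]² + 3, with atanh(.34) = 0.354. Two-sided .05 gives 65.6 and one-sided gives 52.3. The exact calculation gives 65 and 52. At two-sided .005 about 109 are needed.

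**Step 3: rank correlation.** SA3 is planned as nonparametric. Simulation from a bivariate normal (200,000 replicates, n = 25, alpha .05) gives Spearman power at an underlying r of .34 of .35 two-sided and .47 one-sided. Two-sided power reaches .80 at an underlying r of about .56, a population Spearman value of (6/π)·asin(.56/2) = .54.

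**Step 4: margin over the pilot.** At n = 25 and r = .55, two-sided .05, Pearson power is .84. Spearman power is .78 if .55 is the underlying Pearson value, or .82 if .55 is the population Spearman value. At two-sided .005, Pearson power is .54.

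**Step 5: Cohort 2.** 75/3 = 25, but 75/2 = 37.5. At 37 per arm, two-sided .05, the limit is (1.960 + 0.842)/√34 = 0.480, so r = .45 by Fisher and .44 exact. Power at .34 is .55 Pearson and .50 Spearman. At .005 the limit at 37 per arm is .55.

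**Step 6: whole cohort.** At N = 75, two-sided .05, the limit is .32. Power at .34 is .86 Pearson and .81 Spearman.

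**The case against.** The arithmetic at n = 25 is hard to dispute; the stronger objections concern its meaning and the remedy.

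- **The wrong number may be n, not r.** At n = 50, one-sided .05, the exact limit is .344, which rounds to .34. Fifty would be two cells pooled, and the SA3 hypotheses are directional. But 15.2 mentions neither pooling nor a one-sided test, and it says 25 per cell. This remains conjecture, though it is a reason to have the sponsor confirm what was intended.
- **The comparison with .55 is literally true.** For Pearson at alpha .05, .53 is below .55. That stands, but barely. It fails at .005, and for a Spearman test when .55 is taken as the underlying Pearson value.
- **SA3 is split by cohort, not by arm.** This also stands, and a whole-cohort correlation at 75 is adequately powered for .34. It does not rescue a sentence that is explicitly about within-group analyses with 25 per cell.
- **Twenty-five per arm could suit a smaller Cohort 2.** Two arms of 25 make 50 completers, which section 4.1 would allow. But 15.2 still uses 75 and 90 for that cohort, so the section disagrees with itself. The 37-per-arm figure holds only if 75 is reached.
- **Remote working is a contingency and the number unscanned is not given.** True. The effect of missing scans cannot be sized from the documents and is secondary here.
- **Nothing depends on this sentence.** The sample size is argued from eta-squared values, and no decision rule uses the per-arm correlation. This limits the consequence but does not make the figure right.

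**Conclusion.** The concern holds. With 25 per cell, power .80 is reached at r of about .53 two-sided or .48 one-sided at alpha .05, and about .65 at two-sided .005. Neither alpha in 15.2 yields .34. True power at .34 is between about .35 and .52 at alpha .05, depending on test and sidedness, against the claimed .80. The cell size also contradicts the section's own 75 completers in a two-arm Cohort 2.

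The results assume bivariate normal data, a single correlation tested against zero, and complete data on all 25. Participants without the required scans would raise the limit. The failure of .34 does not depend on the assumed alpha, because no conventional level reproduces it. The error should be corrected, but it affects the interpretation of per-arm results and not the sample size.

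**What to change.** In section 15.2:

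1. State which analysis the sentence describes, with its n, alpha, sidedness and type of correlation. If it is per arm in Cohort 1 at two-sided .05, replace .34 with .53 for Pearson. For Spearman, give an underlying r of about .56 (population Spearman about .54). If .005 applies, the Pearson limit is .65.
2. Give Cohort 2 its own two-arm limit: .44 at 37 per arm (Pearson, two-sided .05), higher if fewer are analysed.
3. Base n on participants with the scans needed for a connectivity change, not on session completers.
4. Replace the comparison with the pilot by a statement that at n = 25 the margin over .55 is very small for Pearson at .05, and absent at .005 or for Spearman if .55 is the underlying Pearson value.
5. If the whole-cohort correlation was meant, say so, remove the cell size, and give the limit of .32 at 75 (Pearson, two-sided .05).

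The cost is wording in 15.2, plus a projected number of scanned participants that the sponsor must supply for item 3. Sample size and planned analyses stay as they are. The stated per-arm sensitivity becomes less favourable.

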16.0 Confidentiality

16.1 Data Security:

PROTOCOL TITLE: Increased thalamocortical connectivity in tDCS-potentiated generalization of cognitive

training

VERSION DATE: January 26, 2023

Only research staff will have access to subject information. All records, including those containing identifying information, will be stored in one of the following manners:

- in a private research office in a locked file cabinet;
- in the University of Minnesota supported REDCap database;
- University of Minnesota secured BOX files
- AHC-IS maintained server
- CMRR servers (imaging data)
- secured laboratory (biological samples)

Passwords will be required to access study data stored electronically or in a database. Study data will be available only to select staff that need access to the information to conduct their research duties and to computer system administrators via password.

To minimize the volume of documents containing identifying information, all study documents or data will contain a unique participant ID that will be used when possible.

No copy of the consent form or other research study information will be placed in the participant's medical, employment, or educational records.

17.0 Provisions to Monitor the Data to Ensure the Safety of Participants

17.1 Data Integrity Monitoring.

The PI will be responsible for data accuracy and quality assurance (e.g., data collection, entry, transmission, and analysis), and study management (e.g., enrollment, integrity of study procedures).

The study will be monitored by CTSI in accordance with its institutionally approved monitoring plan.

17.2 Data Safety Monitoring

It is the responsibility of the Principal Investigator to oversee the safety of the study. This safety monitoring will include careful assessment and appropriate reporting of adverse events. Medical monitoring will include a regular assessment of the number and type of serious adverse events.

18.0 Provisions to Protect the Privacy Interests of Participants

18.1 Protecting Privacy:

The study consent form will describe in detail any intrusive, uncomfortable, or unfamiliar questions, procedures, or interactions with researchers or study personnel that the participant will be asked to complete. Furthermore, the study consent form will communicate that it is the participant's right to opt-out of any study procedures or the study as a whole or withdraw from the study at any time and this information will be reiterated and revisited periodically throughout the study in advance of intrusive, uncomfortable, or unfamiliar questions procedures or interactions. Participants will not be compelled or pressured to provide information or specimens or study data that they do not wish to provide.

18.2 Access to Participants:

The research team will not access any medical records from participants.

19.0 Compensation for Research-Related Injury

19.1 Compensation for Research-Related Injury:

In the event that this research activity results in an injury, treatment will be available, including first aid, emergency treatment and follow-up care as needed. Care for such injuries will be billed in the ordinary manner, to the participant or his/her insurance company.

PROTOCOL TITLE: Increased thalamocortical connectivity in tDCS-potentiated generalization of cognitive

training

VERSION DATE: January 26, 2023

19.2 Contract Language: N/A

20.0 Consent Process

20.1 Consent Process (when consent will be obtained):

Prior to the baseline visit, all subjects participating in this study will be required to provide informed consent and HIPAA authorization using an eConsent (electronic consent) form. Only the staff obtaining consent, the subject, and any family members invited by the subject will be present. The research coordinator or other trained research staff will explain the study to the participants. After explaining the study, the participants will be allowed as much time as needed to review the consent document and ask any questions that might arise before making the decision to participate. If necessary, participants can delay participation and return to sign the consent form at a later time. Subjects will be allowed to review the consent form in private for as long as they need. Subjects will be encouraged to ask any and all questions prior to providing consent. Study personnel obtaining consent will emphasize first and foremost that the study is voluntary and will not influence that subject's clinical care or their relationship to the University of Minnesota. No participant will be under legal commitment at the time of their consent or during their participation in the study, and surrogate consent will not be allowed.

The IRB-approved eConsent form will be administered as a REDCap survey. We will follow SOPs from the Psychiatry department on carrying out remote eConsent.

Participants will be offered a physical and/or electronic copy of the consent form and HIPAA authorization to read through during the consent discussion. If the participant agrees to participate, they will sign the consent form and HIPAA authorization.

Participants recruited from Guild Incorporated will be asked to sign an optional Release of Information form provided by Guild Incorporated (attached in ETHOS) as well as to initial an additional, optional section of the informed consent form (provided in ETHOS) that grant permission for the study team to confirm eligibility criteria with the participant's case manager at Guild Incorporated.

Consent to continue in the study will be addressed before each scheduled visit. The participant will be reminded that their participation in this study is completely voluntary and they do not have to continue unless they want to do so. In addition, if at any point during the study the staff has reason to suspect that the individual's capacity to provide consent has diminished (e.g., the participant has increased psychotic symptoms), the study staff may choose to re-administer the UBACC to confirm that the participant has capacity to provide ongoing consent. If the participant does not show capacity to consent, the PI will review their case and determine whether it would be best to withdraw them from the study completely or pause their participation until capacity to consent returns.

20.2 Waiver or Alteration of Consent Process (when consent will not be obtained): N/A

20.3 Non-English Speaking Participants: We will not enroll participants who do not speak English

20.4 Participants Who Are Not Yet Adults (infants, children, teenagers under 18 years of age): We will not enroll participants under 18 years of age.

20.5 Cognitively Impaired Adults (IQ 70-75), or adults with fluctuating or diminished capacity to consent:

PROTOCOL TITLE: Increased thalamocortical connectivity in tDCS-potentiated generalization of cognitive training

VERSION DATE: January 26, 2023

- Cohort 1 subjects are healthy community volunteers.
- Cohort 2 will be subjects who have a psychosis disorder but are clinically stable.
- We will use the UBACC to assess capacity to consent for both cohorts.
- The UBACC will be re-administered at any point if we have reason to believe that there has been a change in capacity to consent due to any of the following:
 - Confusion or disorientation (i.e. not knowing the current time or date)
 - Inability to complete training and tasks that had been done previously

Inability to understand or follow directions

20.6 Adults Unable to Consent: We will not enroll adults unable to consent.

